## **4.0 Study Objective**

The objective of Study M14-431 is to evaluate the efficacy and safety of upadacitinib compared to placebo as induction therapy in subjects with moderately and severely active CD.

## **5.0 Investigational Plan**

### **5.1 Overall Study Design and Plan: Description**

Study M14-431 is a Phase 3, randomized, double-blind, placebo-controlled induction study to evaluate the efficacy and safety of upadacitinib, an orally administered JAK1 inhibitor in adult subjects with moderately to severely active CD who have inadequately responded to or are intolerant to biologic therapy. The study will allow enrollment of up

to 35% of subjects who have demonstrated inadequate response or intolerance to 3 or more biologics.

The study will enroll approximately 625 subjects at approximately 400 study centers worldwide to meet scientific and regulatory objectives without enrolling an undue number of subjects in alignment with ethical considerations.

This study will evaluate one induction dose of upadacitinib (45 mg QD) (Figure 1).

Subjects who consent and meet all of the inclusion criteria and none of the exclusion criteria will be enrolled into this study which encompasses three parts:

- **Part 1:** a randomized, double-blind, placebo-controlled induction period,
- **Part 2:** an open-label, single-arm active induction period, and
- **Part 3:** an Extended Treatment Period for non-responders from Part 1 or Part 2.

### **Part 1**

In Part 1, subjects (n = 495) will be randomized in a 2:1 ratio to upadacitinib 45 mg QD or matching placebo for 12 weeks (Figure 1). The randomization will be stratified by baseline corticosteroid use (yes or no), endoscopic disease severity (SES-CD < 15 and ≥ 15), and number of prior biologic treatments (> 1 and ≤ 1). The data collected from subjects from Part 1 will be used for the primary efficacy analysis.

Visits during the study will occur at Baseline and Weeks 2, 4, 8, and 12/Premature Discontinuation (PD) to collect clinical, endoscopic and laboratory assessments of disease activity.

At Week 12, subjects achieving clinical response, defined as ≥ 30% decrease in average daily very soft or liquid stool frequency (SF) and/or ≥ 30% decrease in average daily abdominal pain (AP) score (both not worse than Baseline) may be eligible to enter the 52-week, double-blind, maintenance portion of Study M14-430.

All subjects who do not achieve clinical response at Week 12 will be able to enroll in Part 3 (Extended Treatment Period) and receive double-blind upadacitinib until Week 24/PD.

Subjects are not eligible to enter Study M14-430 until the ileocolonoscopy procedure at Week 12 has been completed. If the COVID-19 pandemic precludes a subject from undergoing an endoscopy, a subject can enroll in Study M14-430 if clinical response was achieved at Week 12.

[figure not shown]
## **Part 2**

Part 2 is an open-label portion (open-label cohort) of this study. Once enrollment in Part 1 is complete, approximately 130 subjects will be enrolled in Part 2 to receive upadacitinib 45 mg QD for 12 weeks (Figure 1). The objective of Part 2 is to have a sufficient number of subjects with clinical response to be re-randomized in the double-blind maintenance portion of Study M14-430, while minimizing unnecessary exposure to placebo. The data collected from subjects from Part 2 will not be part of the primary efficacy analysis for this study, will use descriptive statistics, and will be reported separately in the clinical study report.

Visits during the study will occur at Baseline and Weeks 2, 4, 8, and 12/PD to collect clinical, endoscopic and laboratory assessments of disease activity.

At Week 12, subjects achieving clinical response may be eligible to enter Study M14-430 (Figure 1). Subjects who do not achieve clinical response at Week 12 will be able to participate in Part 3 (Extended Treatment Period) to receive open-label upadacitinib 30 mg QD until Week 24/PD.

**Figure 1. Study M14-431 Study Design – Part 1 and Part 2**

QD = once daily; Rand = randomization

The study will allow the enrollment of up to 10% of subjects who received a JAK inhibitor prior to study entry if they have not had inadequate response or loss of response.

### Part 3

Part 3 is a 12-week Extended Treatment Period consisting of 3 cohorts for subjects who do not achieve clinical response at Week 12 in Part 1 or Part 2 (Figure 2). The objectives of Part 3 are to offer blinded upadacitinib induction treatment to placebo non-responders from Part 1 and to evaluate delayed clinical response to upadacitinib in subjects who did not initially respond to upadacitinib during Part 1 or Part 2.

[figure not shown]
- **Cohort 1:** Subjects who received placebo in Part 1 and did not achieve clinical response at Week 12 are eligible to receive double-blind induction treatment with upadacitinib 45 mg QD for 12 weeks (until Week 24).
- **Cohort 2:** Subjects who received double-blind upadacitinib in Part 1 and did not achieve clinical response at Week 12 are eligible to receive double-blind upadacitinib 30 mg QD for 12 weeks (until Week 24).
- **Cohort 3:** Subjects who received open-label upadacitinib during Part 2 and did not achieve clinical response at Week 12 are eligible to receive open-label upadacitinib 30 mg QD for 12 weeks (until Week 24).

Subjects in Cohort 1 and 2 will remain blinded to treatment to avoid unmasking the treatment received during Part 1. The data collected from subjects from Part 3 will not be part of the primary efficacy analysis, will use descriptive statistics, and will be reported separately in the clinical study report.

Subjects are not eligible to enter in Part 3 until the Week 12 endoscopy has been completed. If the COVID-19 pandemic precludes a subject from undergoing an endoscopy, a subject can continue into Part 3. Visits will occur at Weeks 16, 20 and 24/PD to collect clinical, endoscopic and laboratory assessments of disease activity.

During Part 3, subjects with persistent symptoms or worsening of CD may be discontinued at any time.

**Figure 2. Study M14-431 Study Design – Part 3**

DB = double-blind; NR = non-responders; OL = open-label; QD = once daily

At Week 24, subjects who achieve clinical response may be eligible to enter Study M14-430. Subjects are not eligible to enter Study M14-430 until the ileocolonoscopy procedure at Week 24 for evaluation of mucosal inflammation has been completed. If the COVID-19 pandemic precludes a subject from undergoing an endoscopy, a subject can enroll if clinical response was achieved at Week 24.

Subjects who do not achieve clinical response at Week 24 will be discontinued from Study M14-431 and will receive standard of care treatment at the investigator's discretion. Subjects who do not achieve clinical response at Week 24 and all subjects who prematurely discontinue the study will have a follow-up visit 30 days from the last dose of study drug to collect information on new or ongoing AEs and laboratory assessments. Subjects will be discontinued from the study if they withdraw consent or if they are deemed unsuitable to continue for any reason by the investigator.

The duration of the study could be up to 33 weeks, including Screening Period (5 weeks), a 12-week double-blind or open-label cohort Induction Period (Part 1 or Part 2), a

12-week Extended Treatment Period (Part 3), and a 30-day follow-up for subjects who do not enroll into Study M14-430.

At the Screening Visit, all subjects will be provided with an electronic diary. Subjects will be instructed and trained on how to record CD-related symptoms (including total and very soft and liquid number of stools and abdominal pain), general well-being and use of anti-diarrheals on a daily basis; and use of medications for endoscopy preparation throughout the study. The very soft and liquid stools are defined as consistency Type 6 or Type 7 based on the Bristol Stool Chart ([Appendix F](#)).

The diary will be reviewed by site personnel with the subject at each visit and for the assessment of the clinical endpoints. At each Study Visit, routine physical examination including evaluation of vital signs, extra-intestinal manifestations (EIMs), presence or absence of fistulas; calculation of CDAI score, total and average daily very soft or liquid SF and average daily AP (very soft or liquid SF and AP entries from the most recent 7-day period prior to each study visit will be used); monitoring of AEs; concomitant medications and laboratory assessments will be performed. The very soft or liquid SF and AP score values represent the unweighted daily averages of the corresponding subscores from the CDAI. Additionally, subjects will complete QoL, CD symptoms, symptoms impact on QoL, and work productivity questionnaires throughout the study as indicated in [Appendix C](#).

Clinical samples for urinalysis, chemistry and hematology, high sensitivity C-reactive protein (hs-CRP), plasma upadacitinib concentrations will be collected. In addition, stool samples for calprotectin analysis will be collected and should be taken before starting bowel preparations for endoscopy.

Subjects will undergo a full colonoscopy (ileocolonoscopy) for evaluation of mucosal inflammation using the SES-CD. All endoscopies will be centrally read to document eligibility at Screening, and for Week 12 and 24/PD assessments. Biopsy to confirm diagnosis (during Screening) or to rule out dysplasia/malignancy may be performed

during the same time points as the endoscopy. Optional exploratory research samples may be taken during the study (see also [Appendix C](#)).

### **Screening Period**

Within 35 days prior to the Baseline Visit, subjects will receive a full explanation of the study design and study procedures, provide a written informed consent, and then undergo the screening procedures outlined in [Appendix C](#). Laboratory values can be re-tested once during the screening period. If the re-tested lab value(s) remain(s) exclusionary, the subject will be considered a screen failure. Redrawing samples if previous samples were unable to be analyzed would not count as a retest since previous result was never obtained.

The length of time between Screening and the Baseline visit must allow time for endoscopy central reading and review of laboratory results. The Screening period will be a minimum of 8 days.

Subjects who have been taking exclusionary medications prior to Screening or Baseline must complete the medication(s) washout within the duration described in the protocol Exclusion Criteria Section [5.2.2](#) prior to the Baseline Visit (i.e., 8-week washout of a biologic therapy). During Screening, biologic drug levels may be optionally assessed at the investigator's discretion as an alternative to completing the required washout period:

- (1) infliximab and natalizumab: may be tested approximately 4 weeks from the last dose;
- (2) adalimumab, certolizumab, golimumab, or vedolizumab: may be tested approximately 6 weeks from the last dose;
- (3) ustekinumab: may be tested approximately 8 weeks from the last dose.

If the biologic drug is not detected, the subject will be considered as eligible and the washout period is not required.

All subjects need to have their average daily very soft or liquid SF and average daily AP score calculated and meeting eligibility criteria before randomization at Baseline.

## **Re-Screen**

Subjects who initially screen fail for the study are permitted to re-screen once following re-consent. For additional re-screenings, AbbVie Therapeutic Area Medical Director (TA MD) approval is required. Laboratory values can be re-tested once during the re-screening period. As appropriate, sites are encouraged to contact the AbbVie TA MD to confirm if subjects should or should not be re-screened. All screening procedures with the possible exceptions noted below will be repeated during re-screening. The subject must meet all of the inclusion criteria and none of the exclusion criteria at the time of re-screening in order to qualify for the study. There is no minimum period of time a subject must wait to re-screen for the study. The re-screening period will be a minimum of 8 days, with the exception of subjects who are re-screened immediately after being screen failed and do not require a repeated endoscopy. The minimum re-screening period for these subjects will be 4 days.

If the subject had a complete initial screening evaluation including the assessment of an Interferon-Gamma Release Assay (IGRA; QuantiFERON-TB [tuberculosis] Gold In Tube test) and/or a purified protein derivative (PPD) test (or equivalent) (or both if required per local guidelines), chest x-ray and electrocardiogram (ECG), tests for hepatitis B virus (HBV), hepatitis C virus (HCV), human immunodeficiency virus (HIV) and beta-D-glucan (Japan only), these tests will not be required to be repeated for re-screening provided the conditions noted in Section 5.2 are met, there are no changes in the subject's medical history that would warrant re-testing, and no more than 90 days have passed since the collection date of the assessment. If a subject is being re-screened within 14 days ( $\leq 14$  days have passed) from the collection date of the previous screening testing, it is not required to repeat Screening testing for chemistry, hematology, urinalysis, serum pregnancy, and *Clostridium difficile* provided that the subject's health status has not changed to warrant a repeat test.

An endoscopy will not be required to be repeated for re-screening provided the conditions noted in Section 5.3.1.1 are met and no more than 45 days have passed between the previous screening endoscopy and Baseline.

All subjects need to have their average daily very soft or liquid SF and average daily AP score calculated and meeting eligibility criteria before randomization at Baseline.

### **12-Week Induction Period – Part 1 and Part 2**

This period will begin at the Baseline Visit and will end at the Week 12 Visit. At the Baseline Visit, subjects who meet all of the inclusion criteria and none of the exclusion criteria described in Section 5.2.1 and Section 5.2.2 will be enrolled into the study. In Part 1, subjects will be randomized to a double-blind induction period. In Part 2, subjects enrolled will receive open-label upadacitinib. During this induction period, all subjects will visit the study site at Weeks 2, 4, 8, and 12/PD, and a  $\pm$  3-day window is permitted around scheduled study visits. The last dose of study drug during this period is taken the day prior to the Week 12 visit.

### **12-Week Extended Treatment Period – Part 3**

This period will begin at Week 12 and will end at the Week 24 Visit. At Week 12, subjects who do not achieve clinical response will enter Part 3. Clinical response is defined as  $\geq$  30% decrease in average daily very soft or liquid SF and/or  $\geq$  30% decrease in average daily AP and both not greater than Baseline. During this period, all subjects will visit the study site at Weeks 16, 20, and 24/PD. A  $\pm$  3-day window is permitted around scheduled study visits. The last dose of study drug during this period is taken the day prior to the Week 24 visit.

### **Premature Discontinuation of Study (Withdrawal of Informed Consent)**

Subjects may withdraw from the study completely (withdrawal of informed consent) for any reason at any time (refer to Section 5.4.1 for additional details). If a subject prematurely discontinues study drug treatment and study participation (withdrawal of informed consent), the procedures outlined for the PD visit should be completed as soon as possible, preferably within 2 weeks of study drug discontinuation. In addition, if the subject is willing, a 30-day follow-up visit (or telephone call if a visit is not possible) should occur to determine the occurrence or status of any new or ongoing AEs/serious

adverse events (SAEs). Subjects who discontinue the study prematurely after randomization will not be replaced.

### **Discontinuation of Study Drug and Continuation of Study Participation**

Subjects may discontinue study drug treatment but may choose to continue to participate in the study (refer to Section 5.4.1 for additional details). Subjects who prematurely discontinue study drug should complete a PD visit as soon as possible, preferably within 2 weeks. Afterwards, subjects should follow the regular visit schedule as outlined in [Appendix C](#), and adhere to all study procedures except for dispensing study drug and PK sample collection, and blood, stool and biopsy sample collection for optional exploratory research. As the subject has discontinued study drug, all rescue and efficacy driven discontinuation criteria no longer apply. If at any point a subject no longer wants to provide assessments (withdrawal of informed consent) following discontinuation of study drug, a second PD visit is not required.

### **Unscheduled Visits**

Unscheduled Visits may occur when the subject is coming in for a medical visit for evaluation and assessment. During Unscheduled Visits, blood samples will be obtained for the laboratory tests listed in [Table 2](#) or for other tests at the investigator's discretion. Visits for dispensing new study drug in case of temperature excursion, loss or damage are not considered an Unscheduled Visit. In addition, visits to only retest a lab will not be considered an Unscheduled Visit.

### **Follow-Up Visit**

A follow-up visit will occur approximately 30 days after the last dose of study drug to obtain information on any new or ongoing AE/SAEs and laboratory assessments.

Subjects will complete the follow-up visit when they have either

- Completed the final study visit and have not enrolled in Study M14-430 OR

- Prematurely discontinued study drug and study participation.

The follow-up visit is not applicable for subjects who discontinued study drug and continued study participation and completed at least one study visit at least 30 days after last study visit.

If a follow-up visit is not possible, a telephone call may be possible to collect information about new or ongoing AEs.

Study visits may be impacted due to the COVID-19 pandemic or any state of emergency or pandemic situation. If visits cannot be conducted onsite due to travel restrictions or other pandemic-related reasons, phone or virtual visits, visits at alternative locations, or changes in the visit frequency and timing of study procedures, among others may be performed. Additional details are provided in the subsequent sections. Every effort should be made to ensure the safety of subjects and site staff, while maintaining the integrity of the study.

## **5.2 Selection of Study Population**

It is anticipated that approximately 625 subjects with active moderately to severely active CD will be enrolled at approximately 400 sites worldwide.

A subject may be enrolled in this study provided that he/she has met all of the inclusion criteria and none of the exclusion criteria specified in this protocol.

### **5.2.1 Inclusion Criteria**

1. Male or female aged  $\geq 18$  and  $\leq 75$  years of age or minimum age of adult consent according to local regulations at Baseline.
2. Confirmed diagnosis of CD for at least 3 months prior to Baseline. Appropriate documentation of biopsy results consistent with the diagnosis of CD, as determined by the investigator, must be available.

3. SES-CD (excluding the presence of narrowing component)  $\geq 6$  (or  $\geq 4$  for subjects with isolated ileal disease), as confirmed by a central reader.
4. Average daily very soft or liquid SF  $\geq 4.0$  **AND/OR** average daily AP score  $\geq 2.0$  at Baseline.
5. Demonstrated an inadequate response or intolerance to one or more of the following biologic agents as defined by:
  - At least one 6-week induction regimen of infliximab ( $\geq 5$  mg/kg intravenous [IV] at Baseline and Weeks 2 and 6),
  - At least one 4-week induction regimen of adalimumab (one 160 mg subcutaneous [SC] dose at Baseline, followed by one 80 mg SC dose at Week 2 [or one 80 mg SC dose at Baseline, followed by one 40 mg SC dose at Week 2, in countries where this dosing regimen is approved]),
  - At least one 4-week induction regimen of certolizumab pegol (400 mg SC at Baseline, and Weeks 2, and 4),
  - At least one 6-week induction regimen of vedolizumab (300 mg IV at Baseline and Weeks 2, and 6),
  - At least one 8-week induction regimen of ustekinumab [260 mg ( $\leq 55$  kg) or 390 mg ( $> 55$  to  $\leq 85$  kg) or 520 mg ( $> 85$  kg) IV, followed by 90 mg SC at Week 8],
  - Recurrence of symptoms during scheduled maintenance dosing following prior clinical response to the above biologics,
  - Intolerance to a biologic may include, but not limited to infusion-related reaction, rash, serum sickness, anaphylaxis, elevated liver enzymes, demyelination, congestive heart failure, infection. Demonstration of intolerance requires no minimum dose or duration of use.
6. Women of childbearing potential (refer to Section 5.2.4), must not have a positive serum pregnancy test at the Screening Visit and must have a negative urine pregnancy test at the Baseline Visit prior to study drug dosing.

Note: subjects with borderline serum pregnancy test at Screening must have absence of clinical suspicion of pregnancy or other pathological cause of a

borderline result and a serum pregnancy test  $\geq 3$  days later to document continued lack of a positive result.

7. If female, subject must be either postmenopausal, OR permanently surgically sterile OR for women of childbearing potential practicing at least one protocol specified method of birth control (refer to Section 5.2.4), that is effective from Baseline Visit through at least 30 days after the last dose of study drug.
8. Subject is judged to be in good health as determined by the principal investigator based upon the results of medical history, laboratory profile, physical examination, chest x-ray, and a 12-lead ECG performed during Screening.
9. Subjects must voluntarily sign and date an informed consent, approved by an Independent Ethics Committee (IEC)/Institutional Review Board (IRB), prior to the initiation of any screening or study-specific procedures and comply with the requirements of this study protocol. In countries where the subject is 18 years-old but not of minimum adult age to consent according to local regulations, a subject's parent or guardian must be willing to provide written informed consent (e.g., Japan < 20 years old).

## **5.2.2 Exclusion Criteria**

A subject will not be eligible for study participation if he/she meets any of the following criteria:

1. Subject with a current diagnosis of ulcerative colitis or indeterminate colitis.

### **Concomitant Medications and Treatments**

2. Subject on CD-related antibiotics who:
  - has not been on stable doses of these medications for at least 14 days prior to Baseline, or

- has discontinued these medications within 14 days of Baseline.
3. Subject on oral aminosalicylates who:
    - has not been on stable doses of these medications for at least 14 days prior to Baseline, or
    - has discontinued these medications within 14 days of Baseline.
  4. Subject on corticosteroids who meet the following:
    - prednisone or equivalent dose > 30 mg/day; or
    - budesonide > 9 mg/day; or
    - has not been on the current course for at least 14 days prior to Baseline and on a stable dose for at least 7 days prior to Baseline.
  5. Subject on MTX who:
    - has not been on the current course for  $\geq 42$  days prior to Baseline, and
    - has not been on a stable dose for  $\geq 28$  days prior to Baseline

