The duration of the study could be up to 33 weeks, including Screening Period (5 weeks), a 12-week double-blind or open-label cohort Induction Period (Part 1 and Part 2), a 12-week Extended Treatment Period (Part 3), and a 30-day follow-up for subjects who do not enroll into Study M14-430.

At the Screening Visit, all subjects will be provided with an electronic diary. Subjects will be instructed and trained on how to record CD-related symptoms (including total and very soft and liquid number of stools and abdominal pain), general well-being and use of anti-diarrheals on a daily basis; and use of medications for endoscopy preparation throughout the study. The very soft and liquid stools are defined as consistency Type 6 or Type 7 based on the Bristol Stool Chart.

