#### **5.2.3.2.1 Concomitant CD-Related Medications (Antibiotics, Aminosalicylates, and/or Methotrexate)**

All subjects receiving a stable dose of CD-related antibiotics, aminosalicylates, or MTX at Baseline should maintain their concomitant treatments, without dose changes through the end of the study. Initiating and/or changing doses of these medications are prohibited during the study. Doses of CD-related antibiotics, aminosalicylates, or MTX may be decreased in the event of moderate-to-severe treatment related toxicities.

Setons are authorized as concomitant therapy in subjects with perianal fistulas and should be documented in the eCRF under concomitant medications.

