2.2 Study Design Overview

This is a Phase 3, randomized, double-blind, placebo-controlled induction study to evaluate the efficacy and safety of upadacitinib, an orally administered JAK1 inhibitor in adult subjects with moderately to severely active CD who have inadequately responded to

or are intolerant to biologic therapy. This study will enroll approximately 645 subjects at approximately 400 study centers worldwide.

[figure not shown]
The biologics approved for the treatment of CD include adalimumab, certolizumab, infliximab, ustekinumab and vedolizumab. The study will allow enrollment of approximately 30% subjects who have had inadequate response or intolerance to 3 or more biologics. The study will allow the enrollment of up to 10% of subjects who received a JAK inhibitor prior to study entry if they have not had inadequate response or loss of response.

The duration of the study could be up to 33 weeks and consists of the following parts:

1. Screening period of up to a maximum of 35 days
2. **Part 1:** a randomized, double-blind, placebo-controlled 12-week induction
3. **Part 2:** an open-label, single-arm active 12-week induction
4. **Part 3:** a 12-week Extended Treatment Period for subjects who do not achieve clinical response at Week 12 of Part 1 or Part 2
5. 30-day follow up period for subjects who do not enroll into Study M14-430

The schematics of the overall study design are shown in [Figure 1](#) (Part 1 and Part 2) and [Figure 2](#) (Part 3).

Figure 1. Study M14-431 Study Design – Part 1 and Part 2

QD = once daily; Rand = randomization

Part 1

In Part 1, subjects (n = 495) will be randomized in a 2:1 ratio to upadacitinib 45 mg QD or matching placebo for 12 weeks (Figure 1). Centralized randomization will be implemented in the study. The randomization will be stratified by baseline corticosteroid use (yes or no), endoscopic disease severity (Simplified Endoscopic Score for Crohn's Disease [SES-CD] < 15 or \geq 15), and number of prior biologic treatments (> 1 or \leq 1). The data collected from subjects from Part 1 will be used for the primary efficacy analysis.

Visits during the study will occur at Baseline and Weeks 2, 4, 8, and 12/Premature Discontinuation (PD) to collect clinical, endoscopic and laboratory assessments of disease activity.

At Week 12, subjects achieving clinical response, defined as \geq 30% decrease in average daily very soft or liquid stool frequency (SF) and/or \geq 30% decrease in average daily

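### Exclusion criterion 5 joins two negated methotrexate conditions with *and*, so read literally it admits subjects whose methotrexate was recently started or changed

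*Protocol*

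**What the plan says.** The lead-in to Protocol section 5.2.2 sets the logic: "A subject will not be eligible for study participation if he/she meets any of the following criteria". Each numbered item is thus a condition that, when true, removes the subject.

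Exclusion 5 concerns subjects on methotrexate and has two bullets. The first is true when the current course is shorter than 42 days and ends "days prior to Baseline and". The second is true when the dose has been stable for fewer than 28 days. Main exclusion 5 in the synopsis (section 1.2) is worded the same way.

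The criteria beside it are built differently. Exclusions 2 and 3 (antibiotics, aminosalicylates) join their bullets with *or*. Exclusion 4 (corticosteroids) puts both requirements under a single negation: "has not been on the current course for at least 14 days prior to Baseline and on a stable dose for at least 7 days". Failing either one excludes.

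Section 5.2.3.2.1 adds a rule for subjects already in the study: "Initiating and/or changing doses of these medications are prohibited during the study". Section 5.5.1 describes background Crohn's therapy as stable.

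**The concern.** Two negated conditions joined by *and* are met only when both requirements fail. The evident aim was that failing either should exclude. As written, a site that follows the text exactly can enrol two groups the criterion was meant to keep out:

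- **(a)** subjects on methotrexate for 42 days or more whose dose changed within 28 days of Baseline;
- **(b)** subjects whose course began 28 to 41 days before Baseline and whose dose has been stable for at least 28 days, which includes every unchanged-dose course started in that window.

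At stake is the premise that background therapy is settled at Baseline, so that change to Week 12 reflects study drug. Deviation reporting is also affected. The two readings classify the same subject differently: eligible under one, an entry-criterion violation under the other. The study plans about 400 sites, and the documents do not show which reading they used.

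**Working it through.** **1. Where the literal and intended rules differ.** Let c be days on the current course and s days on a stable dose, with s ≤ c, in whole days.

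- Literal rule: exclude if c < 42 and s < 28.
- Rule on the exclusion 4 pattern: exclude if c < 42 or s < 28.

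Enumerating all pairs, the rules disagree in exactly two regions: (a) c ≥ 42 with s ≤ 27, and (b) c = 28 to 41 with s ≥ 28. Courses shorter than 28 days are excluded by both, because s ≤ c < 28.

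**2. Whether another rule closes the gap.** The ban in section 5.2.3.2.1 applies during the study and gives no look-back period. Two readings are possible.

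- *The study includes Screening.* The duration statement in Protocol 5.1 counts Screening within the 33 weeks, and SAP 2.2 lists among the study's parts a "Screening period of up to a maximum of 35 days".
- *The study starts at Baseline.* Section 5.2.3.3 names the Screening Visit expressly when it restricts strong CYP3A inhibitors and inducers. The methotrexate rule does not.

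Exclusion 38 (investigator's opinion) and the referral of questions to the sponsor's medical director (section 5.2.3.1) are discretionary and set no methotrexate interval. SAP 8.1 treats methotrexate as a confounding medication only when it is started after study drug is stopped, and SAP 8.2 covers corticosteroids only. Neither handles a start or change before Baseline.

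**3. Days left open.** Let L be the Screening length. For (a), a dose change on days 1 to 27 before Baseline gives 27 days. For (b), taking unchanged-dose courses, a start on days 28 to 41 gives 14 days. If the ban covers Screening, only days beyond L remain:

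- (a): max(0, 27 − L)
- (b): 14 if L ≤ 27, otherwise 41 − L

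| Case | (a) | (b) | Total |
|---|---|---|---|
| Ban starts at Baseline | 27 | 14 | 41 |
| L = 4 (shortest re-screen) | 23 | 14 | 37 |
| L = 8 (shortest Screening) | 19 | 14 | 33 |
| L = 14 | 13 | 14 | 27 |
| L = 21 | 6 | 14 | 20 |
| L = 27 | 0 | 14 | 14 |
| L = 28 | 0 | 13 | 13 |
| L = 35 (longest Screening) | 0 | 6 | 6 |

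The short cases come from section 5.1: "The Screening period will be a minimum of 8 days", and for some re-screened subjects "The minimum re-screening period for these subjects will be 4 days". Group (a) closes once Screening reaches 27 days. Group (b) never closes fully. For example, a dose change 20 days before Baseline with a 14-day Screening passes, as does a start 36 to 41 days before Baseline with the full 35-day Screening.

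**4. How many subjects.** The documents do not give methotrexate use. Assume 5–10% of the 495 Part 1 subjects use it, and that 5–20% of users had a start or change spread evenly over the 41 days.

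- Ban from Baseline: 495 × 0.05 × 0.05 = 1.24, up to 495 × 0.10 × 0.20 = 9.90
- L = 8: multiply by 33/41, giving 1.00 to 7.97
- L = 21: multiply by 20/41, giving 0.60 to 4.83
- L = 35: multiply by 6/41, giving 0.18 to 1.45

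**5. Effect on power.** The plan states at least 95% by Fisher's exact test with 330 and 165 subjects at two-sided 0.05. As an extreme case, let a fraction q of subjects be affected and all become responders in both arms, so p′ = p + q(1 − p). With q = 9.90/495 = 0.02, 12% vs 29% becomes 13.76% vs 30.42%, 20% vs 40% becomes 21.6% vs 41.2%, and 10% vs 25% becomes 11.8% vs 26.5%.

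| Endpoint | q = 0 | 1.45/495 | 7.97/495 | 0.02 |
|---|---|---|---|---|
| PRO remission | 99.40% | 99.34% | 99.01% | 98.89% |
| CDAI remission | 99.61% | 99.58% | 99.44% | 99.39% |
| Endoscopic response | 98.65% | 98.51% | 97.77% | 97.53% |

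The first column confirms the plan's claim. Every other figure also stays above 95%.

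**The case against.** The best answer is that this is a slip of one word whose intent is plain from exclusions 2 to 4, so sites probably applied it as meant. Part 1 is randomised and double-blind, no primary inference turns on the wording, and nothing shows that any subject was enrolled under the literal reading. The head-counts rest on assumed inputs. The plan also has means to limit the consequence: entry-criterion violations are reportable (Protocol 7.0) and tabulated (SAP Appendix A), and SAP 9.3.4 repeats the primary analysis in a per-protocol population.

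Most of this stands, and it is why the point is minor. It does not repair the rule. Eligibility text should not rely on each site correcting it. The deviation table and per-protocol set catch these subjects only if the sponsor applies the intended reading, because under the literal one no entry criterion was breached. No other provision supplies a 28-day or 42-day methotrexate interval.

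**Conclusion.** The concern holds. Exclusion 5 is wrong as written, in section 5.2.2 and in the synopsis, and the ban on changes during the study does not close the gap: 6 to 41 calendar days stay open. The logic follows from the text alone, given whole-day counting and treating an unchanged-dose course as stable from its start.

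The size is small. The estimate of 0.2 to 9.9 subjects out of 495 depends entirely on the assumed methotrexate use, the share with a recent start or change, and the even spread, so it should be read as an order of magnitude. There is no bias in the Part 1 comparison and no material loss of power: at most 1.1 percentage points (98.65% to 97.53%, endoscopic response) in a deliberately extreme case.

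**What to change.** At the next amendment made for other reasons, replace *and* with *or* in exclusion 5 of section 5.2.2 and in synopsis main exclusion 5, or use the single negation of exclusion 4. Amendments need ethics approval (section 9.1), and this correction does not justify one on its own.

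The wording change may not reach Part 1, because Part 2 opens only after Part 1 enrolment is complete and the current amendment resizes Part 2. Part 1's enrolment status is not stated. For subjects already enrolled, list by arm the methotrexate users with a course under 42 days or a dose change within 28 days of Baseline. The dates and doses for the preceding 90 days are already collected (section 5.2.3.1).

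Split the listing by whether the start or change came before or during Screening. Only those during Screening could count as prohibited treatment under section 7.0. Earlier ones could be deviations only as entry-criterion failures, and only if the intended reading is applied, so the sponsor should state which reading it uses. Keep the listing descriptive, with no automatic exclusion from the per-protocol set. The cost is one word in two places and one listing.
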